1 STUDY SUMMARY

Title	A phase 2, randomized study of the tolerability and safety of the OsciPulse device for the prevention of VTE
Short Title	OsciPulse tolerability trial
Phase	Phase 2
Methodology	Randomized, crossover study
Study Duration	4 months
Study Center(s)	Penn Presbyterian Medical Center
	Part 1:
	Primary
	
• To determine the tolerability of the OsciPulse device on healthy individuals.
	Secondary:
	
• To determine the hemodynamic impact of the OsciPulse device on venous blood flow.
	Part 2:
	Primary:
Objectives	
• To determine the tolerability and safety of the OsciPulse device• To evaluate device design with respect to initial clinical safety and device functionality.
	Secondary:
	
• To assess the compliance of the OsciPulse device compared to a standard intermittent pneumatic compression device.• To evaluate the ultrasonographic hemodynamic parameters of the OsciPulse device compared to a standard intermittent pneumatic compression device.

Number of Subjects	Part 1: Three (3) subjects at a single site. Part 2: Fifteen (15) to Twenty (20) subjects at a single site.
Study Population	Part 1: Adults age \geq 40 years healthy volunteers. Exclusion criteria include a current foot or ankle injury, current vascular disease. Part 2: Adults age \geq 18 years admitted to the hospital. Exclusion criteria include contraindications for pneumatic devices, current or previous DVT, and pregnancy.
Investigational Product	OsciPulse mechanical therapy device for the prevention of VTE
Participant Duration	Part 1: Up to 3 hours Part 2: Up to 6-hours in hospital
Description of Facilities	Part 1: Enrollments will take place in the [REDACTED] offices clinical research space. Part 2: Enrollments will take place at the Penn Presbyterian Medical Center (PPMC). [REDACTED] coordinators will conduct bedside data collection in the hospital setting, and chart reviews will be conducted in the [REDACTED] office space located on the [REDACTED] [REDACTED] [REDACTED] at PPMC. This office space is locked with a front door security code.
Reference therapy	Intermittent pneumatic compression device
Statistical Methodology	Part1: Device tolerability will be assessed with a questionnaire focused on the comfort of the OsciPulse device. This data will only be used to validate the tolerability of the device for use in Phase 2 so no statistical analysis will be performed. Part 2: Device tolerability will be measured with a subject questionnaire focused on their comfort for both the OsciPulse device and the intermittent pneumatic compression device. The questions will have continuous visual analog scales to gauge responses, and we will use a paired t-test to evaluate the difference in responses between the OsciPulse device and the reference therapy. We will also monitor subject compliance, and venous valve sinus hemodynamics, when feasible, for each device and a paired t test will be used to compare those values.
Safety Evaluations	Part 1: Adverse events will be collected

Part 2: Adverse events will be collected. Expected AEs in this population include VTE, skin ulceration, peripheral nerve palsy, limb ischemia, and falls.

**Data and Safety
Monitoring Plan**

The Sponsor is responsible for monitoring the data quality and the ongoing safety of subjects.

1.2 Schema

Figure 1. Study Schema

PART 1:

Visit 1

Total Subjects 3: Consent eligible participants

Visit 1

OsciPulse application and study procedure (3 hours)

Proceed from Part 1 to Part 2 if all subjects indicate a lack of “significant discomfort” during Part 1

PART 2:

Visit 1

Total Subjects up to 20: Screen, consent, and randomize eligible participants (within 24 hours from hospital admission)

Visit 2

Intervention 1 and study procedures (0-3 hours)

Visit 3

Intervention 2 and study procedures (3-6 hours)

2 BACKGROUND AND STUDY RATIONALE

This document is a clinical research protocol and the described study will be conducted in full accordance with all applicable University of Pennsylvania Research Policies and Procedures and

Confidential and Proprietary Information of University of Pennsylvania

Protocol V6.0 (1 Jun 2022)

all applicable Federal and state laws and regulations including Good Clinical Practice standards. All episodes of noncompliance will be documented.

2.1 Study Rationale

Venous thromboembolism (VTE) is a major complication occurring in hospitalized subjects. Although anticoagulants and mechanical prophylaxis are commonly used to prevent VTE it remains a leading cause of complications and death in the hospital population. Anticoagulation has been demonstrated to reduce the rates of hospital acquired VTE, but also has increased rates of bleeding complications. Mechanical prophylaxis is typically used together with anticoagulation and has no bleeding risk. However, existing methods of mechanical thromboprophylaxis have some limitations including equivocal efficacy and subject discomfort, which may undermine adherence. The new OsciPulse device was designed based on recent advancements in our understanding of the molecular basis of deep vein thrombosis (DVT) formation to improve the efficacy of mechanical devices in preventing DVT/VTE. The objective of this study is to evaluate device design with respect to initial clinical safety and device functionality.

2.2 Background and Relevant Literature

Venous thromboembolism (VTE), which includes deep-vein thrombosis (DVT) and pulmonary embolism (PE), is the third most common cardiovascular disease with over 1 million new cases per year in the United States¹. VTE is associated with significant morbidity and mortality. The mortality rates after first VTE events are 6% at 30 days and 21% at 1 year². Long term complications include recurrent VTE, post-thrombotic syndrome, and chronic thromboembolic pulmonary hypertension. Approximately 50% of VTE cases are attributable to current or preceding hospitalization, while 12% and 7% are associated with trauma and neurological disease with extremity paresis, respectively³. Immobilization and lower-limb paralysis are independent risk factors for VTE in hospitalized subjects⁴. These well-recognized risks establish the need for effective VTE prevention in high-risk populations. If administered appropriately, a significant number of VTE cases will be preventable by thromboprophylaxis.

Thromboprophylaxis strategies can be categorized into pharmacological (with anticoagulants) and mechanical (with gradual compression stockings [GCS] or intermittent pneumatic compression [IPC] devices). Current clinical practice guidelines suggest using pharmacological thromboprophylaxis over mechanical thromboprophylaxis, and they are often used in conjunction with each other^{5,6}. However, many subjects are not suitable candidates for anticoagulants because of contraindications such as bleeding or thrombocytopenia. In such cases, mechanical thromboprophylaxis provides the only prophylactic option. In suitable acutely ill medical subjects who do not receive pharmacological thromboprophylaxis, the American Society of Hematology VTE guideline suggests mechanical prophylaxis over no prophylaxis. One of the advantages of mechanical prophylaxis is its favorable safety profile. Although possible, the risk of serious harmful effects associated with the currently available options for mechanical thromboprophylaxis, such as limb ischemia or skin ulceration, are exceedingly rare.

The benefit of mechanical prophylaxis, however, remains controversial. In a systematic review of randomized controlled trials (RCT) of stroke subjects⁷, mechanical prophylaxis (GCS and IPC) did not show a significant reduction in VTE or death. In another large RCT in stroke

[figure not shown]
subjects, IPC reduced the risks of asymptomatic DVT and symptomatic proximal or calf DVT. However, the reduction in symptomatic proximal DVT was not significant⁸. In trauma subjects, mechanical thromboprophylaxis reduced the risk of DVT, but not PE or death⁹. Pharmacological prophylaxis was more effective in reducing DVT but had higher risk of minor bleeding⁹. In critically ill subjects, adjunctive use of IPC in addition to pharmacological prophylaxis did not reduce DVT, PE, or death¹⁰. This lack of consistently clear evidence for benefit of mechanical prophylaxis suggests an unmet need for a more effective device to improve the efficacy of mechanical prevention of VTE.

Virchow's triad (venous stasis, endothelial injury, and hypercoagulability) constitutes the mechanistic pathogenesis of VTE. Immobilization leading to venous stasis is a major factor leading to VTE in trauma and stroke subjects.

2.3 Name and Description of the Investigational Product

The study intervention will be the OsciPulse device system. The OsciPulse system is a non-invasive device

2.3.1 Clinical Data to Date

[REDACTED]

2.4 Known Potential Risks

The application of mechanical thromboprophylaxis is a standard practice in many populations and is not considered to pose serious health risk. The risks include mild discomfort, interference with sleep and movement, injury due to falling, skin breakdown ulceration, and worsening of leg ischemia in patients with peripheral arterial disease. Risks of serious events including peripheral nerve palsy, circulatory compromise such as limb ischemia, deep vein thrombosis, pulmonary embolism, pressure ulcers (NPUAP category III and IV), and neuropathy is exceedingly rare but may occur as a result of use of intermittent pneumatic compression. Subjects who are at higher risk of such complications (subjects with pre-existing severe peripheral vascular disease or severe edema of lower extremities) will be excluded from the study. Adverse events of special interests are outlined in section [10.1.4](#)

Additional adverse events expected in the target population include, but are not limited to, infection, bleeding, delirium, thrombosis, shock, respiratory failure, kidney injury, liver injury, and death.

All subjects will be monitored for adverse events over the course of the intervention as outlined in Section [10](#).

2.5 Risk Benefit Assessment

The risks of participating in the study are outweighed by the potential benefits of participating in the study. Study procedures, including, the hemodynamic ultrasonography are not known to pose any additional health risk. If during the hemodynamic ultrasonography a DVT is incidentally identified, the findings will be reported to the subject's treating clinical team. The subject will be removed from the study and further testing or treatment will be at the discretion of the clinical team.

Direct benefits to the participating subjects include the potential benefit of VTE prevention by mechanical thromboprophylaxis. Indirect benefits include collecting more clinical data in terms of safety and tolerability to assist the development of better devices for VTE prevention in the future.

3 STUDY OBJECTIVES

3.1 Primary Objective

Part 1: To determine the tolerability of the OsciPulse device on healthy individuals.

Part 2: To assess the safety and tolerability of the OsciPulse device compared to a standard intermittent pneumatic compression device.

3.2 Secondary Objectives

Part 1: To determine the hemodynamic impact of the OsciPulse device on venous blood flow.

Part 2: To assess the compliance of the OsciPulse device compared to a standard intermittent pneumatic compression device.

To evaluate the ultrasonographic hemodynamic parameters of the OsciPulse device compared to a standard intermittent pneumatic compression device.

4 STUDY PLAN

4.1 Study Design

This is a single site, two-part study. Part 1 is in healthy subjects testing the tolerability of the device. Part 2 is a Phase 2, randomized crossover study in subjects with the potential to develop VTE evaluating the OsciPulse device compared to a standard intermittent pneumatic compression device. Our hypothesis is that the safety and tolerability of the OsciPulse device is equivalent to the standard compression device.

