5.5 Total Number of Subjects and Sites

Part 1: Recruitment will end after 3 subjects have been enrolled.

Part 2: Recruitment will end when no fewer than fifteen (15) evaluable subjects and no greater than twenty (20) evaluable subjects have completed the clinical protocol. In the event a subject begins the clinical protocol, however, does not meet protocol defined requirements of "evaluable" status (see section 9.2, Part 2), the Sponsor reserves the right to replace that subject, which may result in greater than twenty (20) subjects being enrolled. In the unlikely event a disproportionate number of enrolled subjects do not meet the protocol defined requirements for reaching "evaluable" status, the Sponsor may pause the study to enrollment to reevaluate recruitment, inclusion and/or exclusion, or any other activity deemed necessary at the time.

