9.2.1 Primary Endpoint

The primary endpoint of this study is OsciPulse device tolerability compared to the current standard of care device. This endpoint will be measured by quantifying the differences in the responses to the questions on the subject questionnaire for each device. We will compare the visual analog scale ratings for the first 4 questions for each subject between the OsciPulse device and the reference therapy device. There are also 4 questions on the 6-hour questionnaire that ask the participants to directly compare the two devices, to determine the difference in tolerability. The ratings are reported in millimeters and the average differences between the responses will be statistically evaluated using a paired t-test.

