9.2.2 Secondary Endpoints

The secondary endpoints of this study are the hemodynamic effects of each device on venous return dynamics. The hemodynamic endpoints will result from vascular ultrasound measurements

These hemodynamic parameters will be averaged across subjects and the difference between the measurements for each device will be evaluated using a paired t-test. The hemodynamic data will demonstrate the efficacy of the OsciPulse device to create the desired valve sinus reversing flow profile that has been shown in previous clinical studies with healthy volunteers. Confirming this flow in the subject population will demonstrate that the OsciPulse device can be successfully deployed in the clinical setting by clinical staff.

Safety will be monitored by tracking all adverse events during the 3-hour period of wearing each device and evaluated by determining the total number of events under each condition.

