9.2.3 Sample Size and Power Determination

This study is a Phase 2 trial aimed at determining the tolerability and safety of an external device so we will use a convenience sample size of up to 20 enrolled subjects. This was determined in part by allowing that within our targeted population up to 6 subjects could experience an event during the 6-hour study window (discharge, unexpected surgery, loss of consciousness, death), and we would still have 14 subjects with evaluable tolerability and safety data.

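### Part 2 hypothesises equivalence, but the only planned inference is a paired t-test for a difference, with no margin or confidence interval, so the plan cannot support its own hypothesis

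*Combined protocol and SAP*

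**What the plan says.** The hypothesis is in Section 4.1: "Our hypothesis is that the safety and tolerability of the OsciPulse device is equivalent to the standard compression device". No other hypothesis is given for Part 2. The Part 2 primary objective in 3.1 is more neutral: "To assess the safety and tolerability of the OsciPulse device compared to a standard intermittent pneumatic compression device".

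The analysis of tolerability is a test for a difference wherever it appears. In the Study Summary, "we will use a paired t-test to evaluate the difference in responses between the OsciPulse device and the reference therapy". In 9.2.1, "The ratings are reported in millimeters and the average differences between the responses will be statistically evaluated using a paired t-test". Section 9.2.4 repeats the same test. The ratings compared are the first four questions on a 100-mm visual analogue scale (VAS). Section 9.2.1 also mentions four items on the 6-hour questionnaire in which subjects compare the two devices directly.

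Safety is "evaluated by determining the total number of events under each condition" (9.2.2). Section 9.2.7 adds only that adverse events are collected on all randomized subjects.

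On size, 9.2.3 says "we will use a convenience sample size of up to 20 enrolled subjects" and that after losses "we would still have 14 subjects with evaluable tolerability and safety data". Section 5.5 ends recruitment when "no fewer than fifteen (15) evaluable subjects and no greater than twenty (20) evaluable subjects have completed the clinical protocol".

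The documents give no equivalence margin, confidence interval, significance level, sidedness or power.

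**The concern.** A paired t-test takes no difference as its null hypothesis. A small p-value contradicts 4.1. A large one shows only that the data did not rule out zero, and says nothing about how large a difference remains possible. No result of the planned analysis can therefore confirm the stated hypothesis. For safety the gap is wider, because no inference is planned at all.

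What is at stake is the reading of the result. The documents do not say that a non-significant test will be taken as equivalence, but nothing rules it out, and 4.1 invites it. Section 11.4.2 also allows the study to end because the primary endpoint has been met, without saying what would count as met. In a small crossover, a non-significant result reported as equivalent tolerability could hide a difference that subjects notice.

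**Working it through.** **Inputs from the documents.** Evaluable n: 15 to 20 (5.5), or 14 (9.2.3). Design: within-subject comparison of two devices. Endpoint: four VAS questions, 0–100 mm.

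**Assumptions not in the documents.** Two-sided 0.05 level; SD of the within-subject difference 15 to 30 mm; a true difference of 10 mm for illustration; correlation between questions 0 to 0.7; equivalence margins of 10, 15 and 20 mm.

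**1. The plan's own figure.** 20 − 6 = 14, as 9.2.3 states. This is a count after losses. There is no power figure to reproduce.

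**2. Chance that a real difference is non-significant, one question.** The test statistic follows a noncentral t distribution with n − 1 degrees of freedom and noncentrality 10 × √n / SD. The chance sought is the probability that it falls within ± t(0.975, n − 1). For n = 15 and SD 20: noncentrality 10 × 3.873 / 20 = 1.936, critical value 2.145, probability 0.562.

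| n | SD 15 | SD 20 | SD 25 | SD 30 |
|---|---|---|---|---|
| 14 | 0.364 | 0.590 | 0.716 | 0.788 |
| 15 | 0.329 | 0.562 | 0.697 | 0.775 |
| 20 | 0.193 | 0.435 | 0.603 | 0.706 |

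**3. Chance that all four questions are non-significant when all four truly differ by 10 mm.** 200,000 simulated trials; each range runs from correlation 0 to 0.7.

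| n | SD 15 | SD 20 | SD 25 | SD 30 |
|---|---|---|---|---|
| 15 | 0.011–0.129 | 0.101–0.319 | 0.236–0.467 | 0.360–0.569 |
| 20 | 0.001–0.055 | 0.035–0.208 | 0.132–0.362 | 0.248–0.483 |

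**4. What an interval would show.** The 95% half-width is t(0.975, n − 1) × SD / √n. At n = 15 and SD 15: 2.145 × 15 / 3.873 = 8.31 mm.

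| n | SD 15 | SD 20 | SD 25 | SD 30 |
|---|---|---|---|---|
| 14 | 8.66 | 11.55 | 14.43 | 17.32 |
| 15 | 8.31 | 11.08 | 13.84 | 16.61 |
| 20 | 7.02 | 9.36 | 11.70 | 14.04 |

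Even with an observed difference of zero, the data would exclude only differences larger than these.

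**5. Safety.** With zero events in n subjects, the one-sided 95% upper limit on the event rate is 1 − 0.05^(1/n): 19.3% at n = 14, 18.1% at n = 15 and 13.9% at n = 20.

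**6. Power if equivalence were tested properly.** Equivalence is concluded if the 90% interval lies inside the margin; one question, true difference 0.

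| n, margin | SD 15 | SD 20 | SD 25 | SD 30 |
|---|---|---|---|---|
| 15, ±10 mm | 0.582 | 0.199 | 0.046 | 0.009 |
| 15, ±15 mm | 0.958 | 0.735 | 0.432 | 0.199 |
| 15, ±20 mm | 0.999 | 0.958 | 0.806 | 0.582 |
| 20, ±10 mm | 0.780 | 0.393 | 0.123 | 0.026 |
| 20, ±15 mm | 0.992 | 0.887 | 0.653 | 0.393 |
| 20, ±20 mm | 1.000 | 0.992 | 0.928 | 0.780 |

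The paired design is thus not the obstacle: with a wide margin or a small SD it could support equivalence. What is missing is the margin and the rule.

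**The case against.** The best defence is that the harm is conditional. The device comparison is called equivalent once, in a design overview. The objective in 3.1, the endpoint in 9.2.1 and the convenience sample in 9.2.3 all describe an early study that measures differences. Part 2 has no success criterion or go/no-go rule, so the word may express no more than an expectation. This stands as a reason to keep the repair small. It does not remove the mismatch, because the sentence is the only hypothesis for Part 2.

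The size also rests on assumed values. A blanket claim of equivalent tolerability would more naturally need all four questions to be non-significant, and that chance falls to 0.1–5.5% at n = 20 and SD 15. This is fair: how often the test misleads is uncertain. The logical point does not depend on it.

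The analysed numbers are not settled either. Section 9.2.7 collects adverse events on all randomized subjects, whereas 9.3 analyses only those who complete everything, including ultrasound examinations that are elsewhere done only when feasible. The safety denominator could be larger than the evaluable number, and the tolerability number smaller. These are side issues, and so is the conflict between 14 evaluable subjects in 9.2.3 and at least 15 in 5.5. Neither adds to nor weakens this point.

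**Conclusion.** The concern holds. The hypothesis in 4.1 and the analysis in Section 9 do not match, and no result of the analysis as written can support equivalence of tolerability or safety. That conclusion rests on the text alone.

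The practical size depends on the assumed SD and difference. Per question, the risk of missing a true 10 mm difference runs from about one in five (n = 20, SD 15) to about three in four (n = 15, SD 30). For safety, zero events in 15 to 20 subjects cannot carry an equivalence claim. The design and the data remain usable; it is the interpretation that is at risk. This should be fixed before analysis.

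**What to change.** 1. In 4.1, replace the hypothesis with an estimation aim, for example: *Part 2 aims to estimate the difference in tolerability between the OsciPulse device and standard IPC and to describe the safety of each.*
2. In the Study Summary, 9.2.1 and 9.2.4, report for each of the first four VAS questions the mean within-subject difference (OsciPulse minus IPC) with its two-sided 95% confidence interval, and state that p > 0.05 is not evidence of equivalence. The direct-comparison items in 9.2.1 stay as they are.
3. Report safety descriptively, with no equivalence claim.
4. While editing, reconcile the evaluable number in 9.2.3 with that in 5.5.

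This costs protocol wording only. The interval uses the same mean difference and standard error as the planned t-test, so no further data or subjects are needed. The price is that the equivalence claim is dropped.

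If the sponsor prefers to keep that claim for tolerability, the plan must fix and justify a margin in mm before any data review, name the question or questions the claim rests on, conclude equivalence only if their 90% intervals lie inside the margin, and state the power at 15 to 20 evaluable subjects. Under the assumptions above, power for one question at ±10 mm is at most 58% with 15 subjects and 78% with 20, so the margin and a defensible SD would decide whether this route is realistic.
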